9.7. Genetics

A blood sample (10 mL) will be collected for pharmacogenetic analysis as specified in the Schedule of Activities, where local regulations allow.

Samples will not be used to conduct unspecified disease or population genetic research either now or in the future. Samples will be used to investigate variable exposure or response to ixekizumab and to investigate genetic variants thought to play a role in autoimmune disorders. Assessment of variable response may include evaluation of AEs or differences in efficacy.

All samples will be coded with the subject number. These samples and any data generated can be linked back to the subject only by the investigative site personnel.

Samples will be retained for a maximum of 15 years after the last subject visit, or for a shorter period if local regulations and/or ERBs/IRBs impose shorter time limits, for the study at a facility selected by Lilly or its designee. This retention period enables use of new technologies, response to regulatory questions, and investigation of variable response that may not be observed until later in the development of ixekizumab.

Molecular technologies are expected to improve during the 15-year storage period and therefore cannot be specifically named. However, existing approaches include whole genome or exome sequencing, genome wide association studies, multiplex assays, and candidate gene studies.

Regardless of technology utilized, data generated will be used only for the specific research scope described in this section.

9.8. Biomarkers

Not applicable.

9.9. Health Economics

Not applicable.

10. Statistical Considerations and Data Analysis

10.1. Sample Size Determination

Up to approximately 240 subjects may be enrolled so that approximately 216 subjects (108 in the 80-mg ixekizumab commercial formulation [reference] group and 108 in the 80-mg ixekizumab alternate formulation [test] group) complete the study.

A sample size of 108 subjects per treatment group will provide approximately 90% power that the 90% confidence interval (CI) of the geometric mean ratio of maximum observed drug concentration (C_{max}) and area under the concentration versus time curve (AUC) between groups will fall within equivalence range of 0.8 to 1.25. This sample size calculation was based on the assumptions that the PK parameters have log-normal distribution, the percent coefficients of variation (%CV) of C_{max} and AUC are less or equal to 48% (from study RHCT), the expected ratio of geometric means is between 0.997 to 1.04, and the %CV are the same for subjects from each treatment group.

Subjects who are randomized but not administered treatment and subjects who do not complete PK sampling (including day 85) may be replaced so that approximately 216 subjects (108 for each treatment) complete the study.

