5.1. Overall Design

Infection risk

Participants should follow local guidance and clinical research unit (CRU) precautions to minimize risk for COVID-19 infection.

Study RHCU is a Phase 1, subject-blind, 2-arm, randomized, parallel-design study in healthy subjects.

All subjects will be screened within 28 days prior to enrollment. Eligible subjects will be admitted to the CRU on Day -1. At screening, subjects will be stratified into 1 of 3 weight categories (<70.0 kg, 70.0 to 80.0 kg, >80.0 kg). Within the 3 weight categories, subjects will be randomized 1:1 to either 80-mg ixekizumab commercial formulation (reference) or 80-mg ixekizumab alternate formulation (test) and subrandomized 1:1:1 to injection site (arm, thigh, or abdomen) (Table RHCU.2). On Day 1, subjects will receive a single SC dose according to the randomization plan (Table RHCU.2 and Schedule of Activities, Section 2).

The desire is to have approximately equal numbers of subjects in each weight category to avoid a large difference in mean weight between the test and reference formulation groups. A subject population of 72 per weight group is an approximate target with the recommended weight categories selected based on the distribution of weights in the prior studies, RHCS and RHCT. The number of subjects assigned to each formulation and the number of subjects assigned to each site of injection location is desired to be balanced.

Table RHCU.2. Study RHCU Stratification and Randomization Plan

Weight Category (Subjects)	Formulation (80-mg ixekizumab)	Subcutaneous Injection Location ^a	Desired Number of Subjects
Low <70.0 kg (72 subjects)	Commercial (reference)	Arm	12
	Alternate (test)		12
	Commercial (reference)	Abdomen	12
	Alternate (test)		12
	Commercial (reference)	Thigh	12
	Alternate (test)		12
Medium 70.0 kg – 80.0 kg (72 subjects)	Commercial (reference)	Arm	12
	Alternate (test)		12
	Commercial (reference)	Abdomen	12
	Alternate (test)		12
	Commercial (reference)	Thigh	12
	Alternate (test)		12
High >80.0 kg (72 subjects)	Commercial (reference)	Arm	12
	Alternate (test)		12
	Commercial (reference)	Abdomen	12
	Alternate (test)		12
	Commercial (reference)	Thigh	12
	Alternate (test)		12

Abbreviations: RHCU = I1F-MC-RHCU; SC = subcutaneous.

- a A dose of investigational product will consist of 1 SC injection of 80-mg ixekizumab into the arm, thigh, or abdomen. All doses will be administered by trained site staff.

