10.3.2. Pharmacokinetic Analyses

10.3.2.1. Pharmacokinetic Parameter Estimation

Pharmacokinetic parameter estimates for ixekizumab will be calculated by standard noncompartmental methods of analysis.

The primary parameters for analysis will be C_{max} , $AUC(0-t_{last})$ and $AUC(0-\infty)$ of ixekizumab. Other noncompartmental parameters, such as time to maximum drug concentration (t_{max}), half-life associated with the terminal rate constant in noncompartmental analysis ($t_{1/2}$), apparent clearance, and apparent volume of distribution may be reported.

Pharmacokinetic parameters may also be normalized by body weight for summarizing the data and may be summarized by site of injection location using descriptive statistics.

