10.3.2.2. Pharmacokinetic Statistical Inference

Pharmacokinetic parameters will be evaluated to determine the bioequivalence of ixekizumab alternate formulation (test) compared to the ixekizumab commercial formulation (reference). Log-transformed C_{max} and AUC parameters will be evaluated in a linear mixed-effects model

with fixed effects for formulation and a random effect for subject. The treatment differences will be back-transformed to present the ratios of geometric means and the corresponding 90% CI.

The t_{max} will be analyzed using a Wilcoxon rank sum test. Estimates of the median difference based on the observed medians, 90% CIs and p-values from the Wilcoxon rank sum test will be calculated.

Bioequivalence will be concluded if the 90% CI is completely contained within the interval (0.80, 1.25).

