- AUC(0-∞) values where the percentage of the total area extrapolated is more than 20% will be flagged. Any AUC(0-∞) value excluded from summary statistics will be noted in the footnote of the summary table. If AUC(0-∞) cannot be determined for all subjects an alternative AUC measure, such as AUC to a fixed time point, may be used in the assessment exposure between dose groups.

- Half-life ($t_{1/2}$) will be calculated, when appropriate, based on the apparent terminal log-linear portion of the concentration-time curve. The start of the terminal elimination phase for each subject will be defined by visual inspection and generally will be the first point at which there is no systematic deviation from the log-linear decline in serum concentrations. Half-life will only be calculated when a reliable estimate for this parameter can be obtained comprising of at least 3 data points. If $t_{1/2}$ is estimated over a time window of less than 2 half-lives, the values will be flagged in the data listings. Any $t_{1/2}$ value excluded from summary statistics will be documented in the footnote of the summary table.
- A uniform weighting scheme will be used in the regression analysis of the terminal log-linear portion of the concentration-time curve.
- The parameters based on last observed concentration (C_{last}) will be reported.

Individual PK Parameter Rules

- Only quantifiable concentrations will be used to calculate PK parameters with the exception of special handling of certain concentrations reported below the lower limit of quantification (BQL). Serum concentrations reported as BQL will be set to a value of zero when all of the following conditions are met:
 - The compound is non-endogenous.
 - The samples are from the initial dose period for a subject.
 - The time points occur before the first quantifiable concentration.
- All other BQL concentrations that do not meet the above criteria will be set to missing.
- Also, where two or more consecutive concentrations are BQL towards the end of a profile, the profile will be deemed to have terminated and therefore any further quantifiable concentrations will be set to missing for the calculation of the PK parameters unless it is considered to be a true characteristic of the profile of the drug.

Individual Concentration vs. Time Profiles

- Individual concentrations will be plotted utilizing actual sampling times.
- The terminal point selections will be indicated on a semi-logarithmic plot.

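### Is the stated 90% power overstated because three PK parameters must all meet the bioequivalence limits?

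*Protocol*

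**What the plan says.** Protocol 10.1 states that "108 subjects per treatment group will provide approximately 90% power" that the 90% CI of the geometric mean ratio for Cmax and AUC "will fall within equivalence range of 0.8 to 1.25". SAP 7 repeats this. The inputs are given as ranges: log-normal data, CV no greater than 48% (from Study RHCT), equal CVs in the two arms, and "the expected ratio of geometric means is between 0.997 to 1.04". The target is that "approximately 216 subjects (108 for each treatment) complete the study", and up to about 240 may be enrolled to reach it.

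Protocol 10.3.2.1 lists Cmax, AUC(0-tlast) and AUC(0-infinity) after the words "The primary parameters for analysis will be". The decision rule in Protocol 10.3.2.2, also in the synopsis and SAP 9.3.2, is: "Bioequivalence will be concluded if the 90% CI is completely contained within the interval (0.80, 1.25"). It speaks of one CI and does not spell out that each of the three must comply. SAP 9.3.1 adds that, if AUC(0-infinity) cannot be determined for all subjects, "an alternative AUC measure, such as AUC to a fixed time point, may be used".

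**The concern.** One power figure is attached to Cmax and AUC together. A reader may take it as the chance that the study concludes bioequivalence. If that conclusion needs all three CIs inside the limits, the chance of success cannot exceed the power of the weakest parameter, and it falls below that unless the parameters are perfectly correlated. The sample size rests on this figure, so a true joint power several points lower would mean a greater risk of failure than the plan appears to state. The singular wording of the decision rule adds to the doubt, because joint power is undefined until one knows which CIs must pass.

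**Working it through.** **Inputs from the documents.** 108 per arm, 1:1 allocation, limits 0.80 and 1.25, a 90% CI (two one-sided tests at 5%), CV at most 48%, ratio 0.997 to 1.04.

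**Step 1: reproduce the stated figure for one parameter.**
- Log-scale SD = sqrt(ln(1 + 0.48²)) = 0.4553.
- SE of the difference in log means = 0.4553 × sqrt(2/108) = 0.0620, with 2 × 108 − 2 = 214 df.
- Normal approximation at ratio 1.04: power = Φ[(ln 1.25 − ln 1.04)/SE − 1.645] + Φ[(ln 1.04 − ln 0.80)/SE − 1.645] − 1 = 0.902.
- Exact calculation, integrating over the estimated variance, at CV 48%:

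| True ratio | Power, one parameter |
|---|---|
| 1.04 | 90.1% |
| 1.02 | 93.6% |
| 1.00 | 94.8% |
| 0.997 | 94.8% |

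The smallest n per arm giving 90% is 108 at ratio 1.04 and 91 at ratio 0.997. The plan's n is thus the exact minimum for one parameter at CV 48% and ratio 1.04. The 90% is evidently per-parameter power at the least favourable end of both ranges, and it holds for each parameter across those ranges.

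**Step 2: joint power for all three parameters.** The correlations are assumptions, since the documents give none: 0.99 between the two AUCs and 0.6 to 0.95 between Cmax and each AUC. Power was simulated with multivariate normal log differences and Wishart variances, 108 per arm. The CV of 42% is also an assumption, chosen to lie below the stated maximum.

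| Cmax (CV, ratio) | AUCs (CV, ratio) | Joint power |
|---|---|---|
| 48%, 1.04 | 48%, 1.04 | 83.0–87.2% |
| 48%, 1.04 | 48%, 0.997 | 85.8–87.2% |
| 42%, 0.997 | 48%, 1.04 | 88.0–88.6% |
| 48%, 1.04 | 42%, 0.997 | 88.8–89.4% |
| 42%, 1.04 | 48%, 0.997 | 90.5–92.0% |
| 48%, 0.997 | 42%, 1.04 | 90.7–91.9% |
| 48%, 0.997 | 48%, 0.997 | 90.5–92.9% |

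For the first row, the outer cases are 0.9006³ = 73.0% if the three were independent, which is implausible for two AUCs from the same profile, and 90.1% if they were perfectly correlated.

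**Step 3: features of the design that the calculation leaves out.**
- Randomisation is stratified by weight (Protocol 5.1), but the model in SAP 9.3.2 has no weight term. If weight affects exposure, the arms are better balanced than the unadjusted standard error implies, and power is higher. If strata explain 10%, 20% or 30% of log variance (assumed), joint power at the least favourable corner is 85.0–88.7%, 87.3–90.5% or 89.5–92.1%.
- 108 per arm is the completer target, and enrolment may reach about 240, or 120 per arm. At 114 or 120 analysed per arm, the same corner gives 85.3–89.0% or 87.3–90.5%. This is a possibility, not something the plan guarantees.

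**The case for a change.** The strongest case for a change is that 108 has no reserve: it is the bare minimum for one parameter at the values that produced it. Put all three parameters at those same values and joint power is about 3 to 7 points below the printed figure for any plausible correlation. If every CV is 48% and only the ratios differ between Cmax and the AUCs, joint power is still about 86% to 87%. The sponsor took its CV from RHCT, so it could presumably estimate the correlations too, and the clarification would take only a few sentences.

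The arithmetic stands, and so does the observation that the figure carries no per-parameter label. What does not follow is that the plan's power is wrong. The CV and the ratio are given as bounds on a set of parameters. The plan does not assert that every parameter sits at the worst value of both. The inputs that would settle the joint figure are absent from the documents, and a reader who wants it must assume them.

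The points about the decision rule are also minor. With three parameters declared primary, analysts will read the rule as applying to each of them. The alternative AUC is a contingency for incomplete profiles. With Cmax plus a single AUC at the worst corner, joint power is 83.7–87.8%, close to the three-parameter range, so the choice of AUC hardly affects power.

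**Conclusion.** The stated power is correct under the ordinary per-parameter reading: 90.1% at CV 48% and ratio 1.04 with 108 per arm, and higher elsewhere in the stated ranges. Joint power could be as low as about 83% to 87% if all three parameters sit at both limits, or about 90% to 93% at ratio 0.997 and in some mixed cases. These ranges assume Cmax-AUC correlations of 0.6 to 0.95 and an AUC-AUC correlation of 0.99. The documents do not show which case applies, so no shortfall is established.

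Any loss would be one of power only, because requiring every CI to comply does not inflate the chance of a false bioequivalence claim. Labelling the figure as per parameter, and stating that all primary CIs must lie within the limits, would be a courtesy to the reader. It would leave the sample size, model and conclusion as they are. This is a gap that analysts fill sensibly, and no change to the plan follows.

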10.2. Populations for Analyses

10.2.1. Study Participant Disposition

A detailed description of subject disposition will be provided at the end of the study.

10.2.2. Study Participant Characteristics

The subjects' age, sex, weight, height, BMI, race, site of injection, and other demographic characteristics will be recorded and summarized using descriptive statistics.

10.3. Statistical Analyses

Statistical analysis of this study will be the responsibility of Lilly or its designee.

Pharmacokinetic (PK) analyses will be conducted on data from all subjects who receive the complete single dose of ixekizumab and have sufficient evaluable PK. Only subjects who complete the PK sampling schedule to Day 85 will be included in the statistical analysis of PK parameters.

Additional exploratory analyses of the data will be conducted as deemed appropriate, and study results may be pooled with the results of other studies for population PK analysis purposes to avoid issues with post hoc analyses and incomplete disclosures of analyses.

10.3.1. Safety Analyses

10.3.1.1. Clinical Evaluation of Safety

All IP and protocol procedure AEs will be listed, and if the frequency of events allows, safety data will be summarized using descriptive methodology.

The incidence of symptoms for each treatment will be presented by severity and by association with IP as perceived by the investigator. Symptoms reported to occur prior to study entry will be distinguished from those reported as new or increased in severity during the study. Each symptom will be classified by the most suitable term from MedDRA.

The number of IP-related SAEs will be reported.

10.3.1.2. Statistical Evaluation of Safety

Safety parameters that will be assessed include safety laboratory parameters and vital signs parameters. The parameters will be listed and summarized using standard descriptive statistics. Additional analysis will be performed if warranted upon review of the data.

10.3.1.2.1. Statistical Evaluation of Other Safety Parameters

Safety laboratory parameters and vital signs data will be listed and summarized using standard descriptive statistics, where possible. Suicidal ideation and/or behavior and self-injurious behavior with no suicidal intent, based on the C-SSRS, will be listed by subject. Only subjects that show suicidal ideation/behavior or self-injurious behavior without suicidal intent will be included in the listing (i.e., if a subject's answers are all 'no' for the C-SSRS, then that subject will not be displayed). Hospital Anxiety Depression Scale item scores will be listed for subjects with HADS depression subscale ≥ 11 at any time. Additional analysis may be performed if warranted upon review of the data.

10.3.2. Pharmacokinetic Analyses

10.3.2.1. Pharmacokinetic Parameter Estimation

Pharmacokinetic parameter estimates for ixekizumab will be calculated by standard noncompartmental methods of analysis.

The primary parameters for analysis will be C_{max} , $AUC(0-t_{last})$ and $AUC(0-\infty)$ of ixekizumab. Other noncompartmental parameters, such as time to maximum drug concentration (t_{max}), half-life associated with the terminal rate constant in noncompartmental analysis ($t_{1/2}$), apparent clearance, and apparent volume of distribution may be reported.

Pharmacokinetic parameters may also be normalized by body weight for summarizing the data and may be summarized by site of injection location using descriptive statistics.

10.3.2.2. Pharmacokinetic Statistical Inference

Pharmacokinetic parameters will be evaluated to determine the bioequivalence of ixekizumab alternate formulation (test) compared to the ixekizumab commercial formulation (reference). Log-transformed C_{max} and AUC parameters will be evaluated in a linear mixed-effects model

with fixed effects for formulation and a random effect for subject. The treatment differences will be back-transformed to present the ratios of geometric means and the corresponding 90% CI.

The t_{max} will be analyzed using a Wilcoxon rank sum test. Estimates of the median difference based on the observed medians, 90% CIs and p-values from the Wilcoxon rank sum test will be calculated.

Bioequivalence will be concluded if the 90% CI is completely contained within the interval (0.80, 1.25).

10.3.3. Evaluation of Immunogenicity

The frequency and percentage of subjects with preexisting ADAs and with TE-ADAs to ixekizumab will be tabulated. Treatment-emergent ADAs are defined as those with a titer 2-fold (1 dilution) greater than the minimum required dilution if no ADAs were detected at baseline (treatment-induced ADA) or those with a 4-fold (2 dilutions) increase in titer compared to baseline if ADAs were detected at baseline (treatment-boosted ADA). For the TE-ADA subjects, the distribution of maximum titers will be described. The frequency of neutralizing antibodies will also be tabulated in TE-ADA subjects.

The relationship between the presence of antibodies and the safety and PK parameters to ixekizumab may be assessed.

10.3.4. Interim Analyses

No interim analyses are planned for this study. If an unplanned interim analysis is deemed necessary, the Lilly CP, CRP/investigator, or designee will consult with the appropriate medical director or designee to determine if it is necessary to amend the protocol.

11. References

- Snaith RP. The Hospital Anxiety and Depression Scale. *Health Qual Life Outcomes*. 2003;1:29.
- Taltz (ixekizumab) Injection Label. Food and Drug Administration web site. Available at: https://www.accessdata.fda.gov/drugsatfda_docs/label/2019/125521s016lbl.pdf. Accessed October, 22 2019.

12. Appendices

Appendix 1. Abbreviations and Definitions

Term	Definition
%CV	percent coefficients of variation
ADA	antidrug antibody
AE	adverse event: Any untoward medical occurrence in a patient or clinical investigation subject administered a pharmaceutical product that does not necessarily have a causal relationship with this treatment. An AE can therefore be any unfavorable and unintended sign (including an abnormal laboratory finding), symptom, or disease temporally associated with the use of a medicinal (investigational) product, whether or not related to the medicinal (investigational) product.
AI	autoinjector
ALP	alkaline phosphatase
ALT	alanine aminotransferase
AST	aspartate aminotransferase
AUC	area under the concentration versus time curve
BCG	Bacillus Calmette-Guérin
blinding	A procedure in which one or more parties to the study are kept unaware of the treatment assignment(s). Unless otherwise specified, blinding will remain in effect until final database lock. A single-blind study is one in which the investigator and/or his/her staff are aware of the treatment but the subject is not, or vice versa, or when the sponsor is aware of the treatment but the investigator and/or his/her staff and the subject are not. A double-blind study is one in which neither the subject nor any of the investigators or sponsor staff who are involved in the treatment or clinical evaluation of the subjects are aware of the treatment received
BMI	body mass index
CEC	Clinical Events Committee
CI	confidence interval
C_{max}	maximum observed drug concentration
complaint	A complaint is any written, electronic, or oral communication that alleges deficiencies related to the identity, quality, purity, durability, reliability, safety or effectiveness, or performance of a drug or drug delivery system.
compliance	Adherence to all the study-related requirements, good clinical practice (GCP) requirements, and the applicable regulatory requirements.
confirmation	A process used to confirm that laboratory test results meet the quality requirements defined by the laboratory generating the data and that Lilly is confident that results are accurate. Confirmation will either occur immediately after initial testing or will require that samples be held to be retested at some defined time point, depending on the steps required to obtain confirmed results.

CP	Clinical Pharmacologist
CRF	case report form
CRP	Clinical Research Physician: Individual responsible for the medical conduct of the study. Responsibilities of the CRP may be performed by a physician, clinical research scientist, global safety physician or other medical officer.
CRU	clinical research unit
C-SSRS	Columbia Suicide Severity Rating Scale
ECG	electrocardiogram
eCRF	electronic case report form
ELISA	enzyme-linked immunosorbent assay
enroll	The act of assigning a subject to a treatment. Subjects who are enrolled in the study are those who have been assigned to a treatment.
enter	Subjects entered into a study are those who sign the informed consent form directly or through their legally acceptable representatives.
ERB	Ethical Review Board
GCP	good clinical practice
HADS	Hospital Anxiety and Depression Scale
HIV	human immunodeficiency virus
IB	Investigator's Brochure
IBD	inflammatory bowel disease
IL	interleukin
IL-17A	interleukin 17A
informed consent	A process by which a subject voluntarily confirms his or her willingness to participate in a particular study, after having been informed of all aspects of the study that are relevant to the subject's decision to participate. Informed consent is documented by means of a written, signed and dated informed consent form.
investigator	A person responsible for the conduct of the clinical study at a study site. If a study is conducted by a team of individuals at a study site, the investigator is the responsible leader of the team and may be called the principal investigator.
IP	investigational product: A pharmaceutical form of an active ingredient or placebo being tested or used as a reference in a clinical study, including products already on the market when used or assembled (formulated or packaged) in a way different from the authorized form, or marketed products used for an unauthorized indication, or marketed products used to gain further information about the authorized form.

ISR	injection site reaction
Legal Representative	An individual or judicial or other body authorized under applicable law to consent, on behalf of a prospective subject, to the subject's participation in the clinical study.
Lilly	Eli Lilly and Company
MedDRA	Medical Dictionary for Regulatory Activities
randomize	The process of assigning subjects/patients to an experimental group on a random basis.
PE	physical examination
PFS	prefilled syringe
PK	pharmacokinetic
Ps	plaque psoriasis
PsA	psoriatic arthritis
RHCA	Study I1F-MC-RHCA
RHCK	Study I1F-MC-RHCK
RHCS	Study I1F-MC-RHCS
RHCT	Study I1F-MC-RHCT
RHCU	Study I1F-MC-RHCU
SAE	serious adverse event
SC	subcutaneous
screen	The act of determining if an individual meets minimum requirements to become part of a pool of potential candidates for participation in a clinical study.
SUSARs	suspected unexpected serious adverse reactions
TBL	total bilirubin level
TE-ADA	treatment-emergent antidrug antibody
TEAE	treatment-emergent adverse event: Any untoward medical occurrence that emerges during a defined treatment period, having been absent pretreatment, or worsens relative to the pretreatment state, and does not necessarily have to have a causal relationship with this treatment.
t_{1/2}	half-life associated with the terminal rate constant in noncompartmental analysis
t_{max}	time to maximum drug concentration

ULN upper limit of normal

VAS visual analog scale

